9.8 Multiplicity

There are 3 pair-wise treatment group comparisons that may be tested to address the primary hypothesis. Testing will start with the 300 mg MK-3655 Q4W, then proceed to the 100 mg MK-3655 Q4W dose, and then to the 50 mg MK-3655 Q4W dose, stopping after the first test with a p -value >0.025 (1-sided).

The multiplicity strategy strongly controls the Type I error at 2.5% (one-sided) to address the primary hypothesis.

9.9 Sample Size and Power Calculations

9.9.1 Efficacy

Through 24 weeks post-randomization, drop-out is expected to be approximately 10% in each treatment group. The drop-out through 52 weeks post-randomization is expected to be approximately 15% in each treatment group. However, based on the approach to missing data, all 82 randomized participants per group are expected to be included in the primary and key secondary analyses and are the basis for sample size and power calculations.

The sample size was chosen based on the proportion of participants with NASH resolution without worsening in fibrosis after 52 weeks. Assuming the true proportion with this endpoint is 35% for each MK-3655 dose versus 12% for placebo, the assumed proportion using a non-completer = failure approach would be 30% for each MK-3655 versus 10% for placebo. Under these assumed proportions, a sample size of 82 participants per group provides 90% power to demonstrate superiority for each of the 3 pair-wise treatment comparisons using a one-sided $\alpha = 0.025$.

With respect to the secondary endpoint of percent relative reduction from baseline in LFC after 24 weeks, a sample size of 82 participants per group provides $>99\%$ power (standard deviation = 20% and assumed mean difference over placebo $\geq 40\%$) using a one-sided $\alpha = 0.025$.

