Interim Analyses	
A single IA is planned for administrative purposes and to assess futility. The IA is planned to be performed once ≥ 25 participants per group have completed an MRI-PDF at the Week 24 post-randomization assessment. Results will be reviewed by an eDMC. Key endpoints to be evaluated include LFC (efficacy), body weight, AEs, and PDLC in laboratory parameters.
 
The study may stop for futility if the posterior probability is $< 5\%$ that the true mean difference (MK-3655 minus placebo) in percent reduction from baseline in LFC is $\geq 40\%$ for all active treatment groups.

Multiplicity	
There are 3 pair-wise treatment group comparisons that may be tested to address the primary hypothesis. Testing will be performed in order of descending dose and will stop with the first comparison that has a one-sided p-value > 0.025.

Sample Size and Power	
The sample size was chosen based on the proportion of participants with NASH resolution without worsening in fibrosis after 52 weeks. Assuming the proportion with this endpoint based on a non-completer = failure approach is 30% for each MK-3655 dose/modality versus 10% for placebo, a sample size of 82 participants per group provides 90% power for each of the 3 pair-wise treatment comparisons using a one-sided $\alpha = 0.025$.

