9.6.1.1 Primary Efficacy Endpoint

The primary approach for addressing the primary hypothesis will use the stratified M&N method with minimum risk weights [Mehrotra, D. V. 2000]. The proportion of participants achieving NASH resolution without worsening in fibrosis will be summarized by treatment group. The difference in proportion, 95% CI, and *p*-values will be provided to address the primary objective and associated hypothesis (MK-3655 minus placebo; 3 pair-wise comparisons).

Participants with missing histology data at Week 52 will be considered as not achieving the primary efficacy endpoint.

A *p*-value for the comparison of MK-3655 versus placebo ≤ 0.025 (one-sided) will be considered statistically significant contingent on the multiplicity strategy (Section 9.8).

Some participants may discontinue before their Week 52 assessment and have a histologic assessment post-randomization (Day 1). For the analysis at the Week 52 timepoint, the Week 52 assessment used in the analysis will be the assessment that is closest to the Week 52 nominal visit (Day 364) that is on or after relative Day 84.

Endpoint response assessment will be based on a centrally-read assessment of both baseline and end of study specimens, blinded to time, and performed when the end of study specimen is available. This post-randomization assessment of the baseline specimen will be considered as the primary histologic baseline assessment for assessing treatment response, though it will not impact on the inclusion of participants in the primary approach to analysis of the primary efficacy endpoint.

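### The stated 90% power for each dose is per-comparison power; under the fixed testing sequence, power to declare superiority is about 82–85% for 100 mg and 76–80% for 50 mg

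*Combined protocol and SAP*

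**What the plan says.** Section 9.9.1 takes one response rate for all active groups: "the assumed proportion using a non-completer = failure approach would be 30% for each MK-3655 versus 10% for placebo". From that it concludes that "a sample size of 82 participants per group provides 90% power to demonstrate superiority for each of the 3 pair-wise treatment comparisons", at a one-sided alpha of 0.025. The Sample Size and Power row of Section 9.1 says the same: "a sample size of 82 participants per group provides 90% power for each of the 3 pair-wise treatment comparisons".

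The decision rule is sequential. Section 9.8 sets the order: "Testing will start with the 300 mg MK-3655 Q4W, then proceed to the 100 mg MK-3655 Q4W dose". The lowest dose, 50 mg, comes last, and the sequence ends at the first comparison whose one-sided p-value exceeds 0.025. The Multiplicity row of Section 9.1 agrees: "Testing will be performed in order of descending dose and will stop with the first comparison" that misses that threshold. Section 9.6.1.1 ties significance to this rule: a one-sided p-value of 0.025 or less "will be considered statistically significant contingent on the multiplicity strategy (Section 9.8").

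The formal hypothesis in Section 3 (H1) needs only one dose to be superior to placebo. Nowhere does the plan call the 90% a per-comparison figure or give power for the second and third steps.

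**The concern.** Section 9.9.1 speaks of the power to demonstrate superiority for each comparison. Under Sections 9.6.1.1 and 9.8, superiority of 100 mg is demonstrated only if the 300 mg and 100 mg tests both reject, and superiority of 50 mg only if all three reject. The relevant powers are therefore joint probabilities, and these must be lower than the 90% for a single test.

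A reader who takes Section 9.9.1 at face value will think that each dose has a 10% chance of missing a formal result when the assumed effect is real. Study goals in Sections 2.1 and 4.2 include identifying doses for further development and supporting Phase 3 dose selection, so the chance of a confirmatory result at the lower doses matters to that reader.

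**Working it through.** **Inputs.** Response 30% for each MK-3655 dose and 10% for placebo, with non-completers counted as failures (9.9.1); 82 per group (9.1, 9.9.1); one-sided alpha 0.025 at every step, in the order 300, 100, 50 mg (9.8); one placebo group shared by all comparisons. The plan does not name its power method, so two were used.

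**Step 1. Reproduce the stated 90%.** Pooled-variance normal approximation, with average rate (0.30 + 0.10)/2 = 0.20:

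- Standard error under the null: √(2 × 0.20 × 0.80 / 82) = 0.06247
- Critical difference: 1.96 × 0.06247 = 0.1224
- Standard error under the alternative: √((0.30 × 0.70 + 0.10 × 0.90) / 82) = √(0.30/82) = 0.06049
- z = (0.20 − 0.1224) / 0.06049 = 1.282, so power = Φ(1.282) = 90.0%

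The stated figure is therefore the power of one two-group comparison. It is also the power of the 300 mg test, because that test comes first and depends on nothing else.

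**Step 2. Joint power, normal approximation.** The shared placebo group gives a correlation between any two comparisons of 0.09 / (0.09 + 0.21) = 0.30. With u the standardised placebo error, the probability that the first k tests all reject is

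∫ φ(u) · [Φ((1.282 − √0.30 · u) / √0.70)]^k du

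- k = 1 (300 mg): 90.0%
- k = 2 (300 and 100 mg): 82.2%
- k = 3 (all three): 75.8%

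The conventional correlation of 0.50 gives about 83% and 78% for k = 2 and 3. Treating the tests as independent would give 0.90² = 81.0% and 0.90³ = 72.9%.

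**Step 3. Joint power, exact enumeration.** This uses the unstratified Miettinen–Nurminen score test. Let q(x₀) be the probability that an active group at 30% rejects when placebo has x₀ responders. The probability that the first k tests all reject is

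Σ over x₀ of Bin(x₀; 82, 0.10) · q(x₀)^k

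| Dose (step) | Pooled normal | Exact M&N | Shortfall from stated 90% |
|---|---|---|---|
| 300 mg (1) | 90.0% | 91.1% | none |
| 100 mg (2) | 82.2% | 84.7% | 7.8 / 5.3 points |
| 50 mg (3) | 75.8% | 79.8% | 14.2 / 10.2 points |

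The chance of not declaring superiority is therefore 15.3–17.8% for 100 mg and 20.2–24.2% for 50 mg, against an implied 10%.

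**Step 4. Dependence on equal rates.** Section 4.3.3 predicts a sub-maximal effect of 50 mg on liver fat and other biomarkers, and says that the link to histology is unknown. The plan gives no lower histologic rate for 50 mg. As illustration only, keep 300 mg and 100 mg at 30% and assume a lower rate for 50 mg:

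- 28% at 50 mg: 71.7% (normal) or 75.9% (exact)
- 25% at 50 mg: 62.4% (normal) or 66.4% (exact)

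The planned stratified test with minimum risk weights was not computed, because the documents give no rates by stratum.

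**The case against.** The strongest reply is that nothing stated is numerically wrong. Quoting power for each pair-wise comparison at full alpha is the usual way to give per-comparison power, and the 90% reproduces. The sequence is disclosed in Section 9.8, and in Section 9.1 it stands directly above the power row. Section 9.7 separates probabilities for a given treatment group from those for all doses together, which supports reading the power figure as per comparison.

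In addition, H1 needs one dose only. Under the sequence it is met through 300 mg, so its power is about 90% as claimed. The plan sets no power target for the later steps, and Section 9.6.1.1 says that differences, confidence intervals and p-values "will be provided to address the primary objective and associated hypothesis (MK-3655 minus placebo; 3 pair-wise comparisons"), whether or not the sequence stops. For a Phase 2b dose-finding study those estimates do much of the work.

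Most of this stands, and it limits the consequence. It does not rescue the sentence. Section 9.9.1 claims power to demonstrate superiority, and Sections 9.6.1.1 and 9.8 define what that takes. The care shown in Section 9.7 in separating single-group from joint probabilities is what is missing here.

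A smaller objection is that the exact shortfalls are measured from a stated 90% that matches the normal approximation. Against the exact single-test figure of 91.1% they are 6.4 points (91.1 − 84.7) and 11.3 points (91.1 − 79.8). The conclusion is the same either way.

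**Conclusion.** The concern holds. The 90% is right as per-comparison power and as the power for 300 mg and H1, but the plan's own testing rule does not deliver it for the two lower doses. There, power to declare superiority is about 82–85% (100 mg) and 76–80% (50 mg). This is a misstatement of what the design achieves, not a calculation error and not a threat to validity: Type I error, sample size, power for H1 and the reported estimates do not change.

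The figures rest on equal 30% response at every dose, 10% on placebo, one shared placebo group and an unstratified test. If 50 mg is less effective on histology than the higher doses, its power is lower still.

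**What to change.** Keep the sample size, alpha and testing order. Reword Section 9.9.1 and the matching row of Section 9.1 along these lines:

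> With 82 participants per group, power is 90% for the 300 mg comparison and hence for H1; 90% is the marginal power of any single comparison with placebo. Under the fixed sequence of Section 9.8, and assuming the same response rate at every dose, power to demonstrate superiority is approximately 82% for 100 mg and 76% for 50 mg (pooled-variance normal approximation, shared placebo group).

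The 82% and 76% come from the method that reproduces the plan's 90%. If the sponsor used another method, all three figures should come from that one method, and it should be named. Unstratified exact Miettinen–Nurminen, for example, gives 91%, 85% and 80%.

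The cost is a wording change in two places and a less favourable stated figure for the two lower doses. No hypothesis or planned analysis changes.

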9.9.2 Safety

Given the sample size of 82 per group, [Table 9](#) provides examples of minimum differences in proportions in AEs between each MK-3655 dose and placebo that would have a 95% CI that excludes zero based on the M&N method [Miettinen, O. and Nurminen, M. 1985].

Table 9 Examples of AE Incidences for Which the 95% CI for the Difference Would Exclude Zero

MK-3655 n/N (%)	Placebo n/N (%)
7/82 (9%)	1/82 (1%)
10/82 (12%)	3/82 (4%)
15/82 (18%)	6/82 (7%)

M&N=Miettinen and Nurminen method; n=sample size; N=population size.
Based on the M&N method [Miettinen, O. and Nurminen, M. 1985].

9.10 Subgroup Analyses

Primary and key secondary efficacy endpoints will be summarized for each of the following baseline defined subgroups:

- Concurrent diagnosis of T2DM at the time of randomization (Yes or No)
- Fibrosis score (Stage 2 or Stage 3)
- Region (Japan, East Asia excluding Japan, or Other)
- Age (≥ 65 years vs < 65 years)
- BMI (> 30 kg/m² vs ≤ 30 kg/m²)
- Region (to be defined in the sSAP)
- LFC ($> 20\%$ vs $\leq 20\%$)
- Sex (male vs female)

9.11 Compliance (Medication Adherence)

Compliance and accountability data for study intervention will be collected during the study. Any deviation from protocol-directed administration will be reported. The primary definition of compliance is defined as the proportion of participants who received the expected number of injections over the duration of time that they were in the study divided by the total number of participants receiving at least one injection. Further detail will be provided in the sSAP.

Drug accountability data for study treatment will be collected during the study. Compliance with study treatment administration will be measured by subjects: (1) receiving unscheduled study agent injections; (2) missing an injection. Numbers and percentages of subjects and

injection visits with any deviation in these measures will be reported for all randomized participants.

9.12 Extent of Exposure

The extent of exposure will be summarized as duration of treatment in terms of number of injections. Dose interruption will be summarized. Summary statistics will be provided on extent of exposure for the APaT population. Further detail will be provided in the sSAP.

10 SUPPORTING DOCUMENTATION AND OPERATIONAL CONSIDERATIONS

10.1 Appendix 1: Regulatory, Ethical, and Study Oversight Considerations

10.1.1 Code of Conduct for Clinical Trials

Merck Sharp & Dohme LLC, Rahway, NJ, USA (MSD)

Code of Conduct for Interventional Clinical Trials

I. Introduction

A. Purpose

MSD, through its subsidiaries, conducts clinical trials worldwide to evaluate the safety and effectiveness of our products. As such, we are committed to designing, implementing, conducting, analyzing, and reporting these trials in compliance with the highest ethical and scientific standards. Protection of participants in clinical trials is the overriding concern in the design and conduct of clinical trials. In all cases, MSD clinical trials will be conducted in compliance with local and/or national regulations, (including all applicable data protection laws and regulations), and International Council for Harmonisation Good Clinical Practice (ICH-GCP), and also in accordance with the ethical principles that have their origin in the Declaration of Helsinki.

B. Scope

Highest ethical and scientific standards shall be endorsed for all clinical interventional investigations sponsored by MSD irrespective of the party (parties) employed for their execution (e.g., contract research organizations, collaborative research efforts). This Code is not intended to apply to trials that are observational in nature, or which are retrospective. Further, this Code does not apply to investigator-initiated trials, which are not under the full control of MSD.

II. Scientific Issues

A. Trial Conduct

1. Trial Design

Except for pilot or estimation trials, clinical trial protocols will be hypothesis-driven to assess safety, efficacy and/or pharmacokinetic or pharmacodynamic indices of MSD or comparator products. Alternatively, MSD may conduct outcomes research trials, trials to assess or validate various endpoint measures, or trials to determine patient preferences, etc.

The design (i.e., participant population, duration, statistical power) must be adequate to address the specific purpose of the trial and shall respect the data protection rights of all participants, trial site staff and, where applicable, third parties. Participants must meet protocol entry criteria to be enrolled in the trial.

2. Site Selection

MSD selects investigative sites based on medical expertise, access to appropriate participants, adequacy of facilities and staff, previous performance in clinical trials, as well as budgetary considerations. Prior to trial initiation, sites are evaluated by MSD personnel (or individuals acting on behalf of MSD) to assess the ability to successfully conduct the trial.

3. Site Monitoring/Scientific Integrity

Investigative trial sites are monitored to assess compliance with the trial protocol and Good Clinical Practice (GCP). MSD reviews clinical data for accuracy, completeness, and consistency. Data are verified versus

source documentation according to standard operating procedures. Per MSD policies and procedures, if potential fraud, scientific/research misconduct, privacy incidents/breaches or Clinical Trial-related Significant Quality Issues are reported, such matters are investigated. When necessary, appropriate corrective and/or preventative actions are defined and regulatory authorities and/or ethics review committees are notified.

B. Publication and Authorship

Regardless of trial outcome, MSD commits to publish the primary and secondary results of its registered trials of marketed products in which treatment is assigned, according to the pre-specified plans for data analysis. To the extent scientifically appropriate, MSD seeks to publish the results of other analyses it conducts that are important to patients, physicians, and payers. Some early phase or pilot trials are intended to be hypothesis-generating rather than hypothesis testing; in such cases, publication of results may not be appropriate since the trial may be underpowered and the analyses complicated by statistical issues such as multiplicity.

MSD's policy on authorship is consistent with the recommendations published by the International Committee of Medical Journal Editors (ICMJE). In summary, authorship should reflect significant contribution to the design and conduct of the trial, performance or interpretation of the analysis, and/or writing of the manuscript. All named authors must be able to defend the trial results and conclusions. MSD funding of a trial will be acknowledged in publications.

III. Participant Protection

A. Regulatory Authority and Ethics Committee Review (Institutional Review Board [IRB]/Independent Ethics Committee [IEC])

All protocols and protocol amendments will be submitted by MSD for regulatory authority acceptance/authorization prior to implementation of the trial or amendment, in compliance with local and/or national regulations.

The protocol, protocol amendment(s), informed consent form, investigator's brochure, and other relevant trial documents must be reviewed and approved by an IRB/IEC before being implemented at each site, in compliance with local and/or national regulations. Changes to the protocol that are required urgently to eliminate an immediate hazard and to protect participant safety may be enacted in anticipation of ethics committee approval. MSD will inform regulatory authorities of such new measures to protect participant safety, in compliance with local and/or national regulations.

B. Safety

The guiding principle in decision-making in clinical trials is that participant welfare is of primary importance. Potential participants will be informed of the risks and benefits of, as well as alternatives to, trial participation. At a minimum, trial designs will take into account the local standard of care.

All participation in MSD clinical trials is voluntary. Participants enter the trial only after informed consent is obtained. Participants may withdraw from an MSD trial at any time, without any influence on their access to, or receipt of, medical care that may otherwise be available to them.

C. Confidentiality

MSD is committed to safeguarding participant confidentiality, to the greatest extent possible, as well as all applicable data protection rights. Unless required by law, only the investigator, Sponsor (or individuals acting on behalf of MSD), ethics committee, and/or regulatory authorities will have access to confidential medical records that might identify the participant by name.

D. Genomic Research

Genomic research will only be conducted in accordance with a protocol and informed consent authorized by an ethics committee.

IV. Financial Considerations

A. Payments to Investigators

Clinical trials are time- and labor-intensive. It is MSD's policy to compensate investigators (or the sponsoring institution) in a fair manner for the work performed in support of MSD trials. MSD does not pay incentives to enroll participants in its trials. However, when enrollment is particularly challenging, additional payments may be made to compensate for the time spent in extra recruiting efforts.

MSD does not pay for participant referrals. However, MSD may compensate referring physicians for time spent on chart review and medical evaluation to identify potentially eligible participants.

B. Clinical Research Funding

Informed consent forms will disclose that the trial is sponsored by MSD, and that the investigator or sponsoring institution is being paid or provided a grant for performing the trial. However, the local ethics committee may wish to alter the wording of the disclosure statement to be consistent with financial practices at that institution. As noted above, all publications resulting from MSD trials will indicate MSD as a source of funding.

C. Funding for Travel and Other Requests

Funding of travel by investigators and support staff (e.g., to scientific meetings, investigator meetings, etc.) will be consistent with local guidelines and practices.

V. Investigator Commitment

Investigators will be expected to review MSD's Code of Conduct as an appendix to the trial protocol, and in signing the protocol, agree to support these ethical and scientific standards.

10.1.2 Financial Disclosure

Financial Disclosure requirements are outlined in the US Food and Drug Administration Regulations, Financial Disclosure by Clinical Investigators (21 CFR Part 54). It is the Sponsor's responsibility to determine, based on these regulations, whether a request for Financial Disclosure information is required. It is the investigator's/subinvestigator's responsibility to comply with any such request.

The investigator/subinvestigator(s) agree, if requested by the Sponsor in accordance with 21 CFR Part 54, to provide his/her financial interests in and/or arrangements with the Sponsor to allow for the submission of complete and accurate certification and disclosure statements. The investigator/subinvestigator(s) further agree to provide this information on a Certification/Disclosure Form, commonly known as a financial disclosure form, provided by the Sponsor. The investigator/subinvestigator(s) also consent to the transmission of this information to the Sponsor in the United States for these purposes. This may involve the transmission of information to countries that do not have laws protecting personal data.

